## 3.3 Study Population

The study involves consenting adults 18 years of age and older with a large, complex abdominal wall hernia. The specific definition of this population is described in the Inclusion/Exclusion criteria.

Given the 1:1 randomized nature of the clinical trial and to preserve the inherent characteristics of the randomization, analysis by intention-to-treat (ITT) is chosen. This type of analysis compares the study groups in terms of the treatment to which they were randomly allocated, irrespective of the treatment they actually received or other trial outcomes. Regardless of protocol deviations and participant compliance or withdrawal, analysis is performed according to the assigned treatment group. This type of analysis will also help to demonstrate if there is superiority of one implant over the other.

If there is no superiority of one implant over the other, analysis will be performed using the same outcomes to assess if there is equivalence between both implants. This will demonstrate that there is no clinically significant difference between the two treatment arms.

#### 3.4 Interim Analysis

Post Market Surveillance Interim Analysis

As this is a post-market study, the data will also support RTI Surgical requirements for post-market surveillance. At the request of regulatory agencies, interim data will be summarized approximately every 12 months. This summary will list the clinical outcomes as well as any adverse events that have been reported since the start of the study. While patient data (no personal identifiers, only subject number will

be included) will be un-blinded for this summary, this will only be for internal use at RTI and for appropriate regulatory or notified bodies. The patient and treating independent reviewer will remain blinded throughout the course of this study.

#### IV. Potential Risks

The planned surgical intervention for the treatment of the ventral hernia is part of the routine clinical care for the patient. Therefore, the surgical intervention itself is associated with several risks to the patient (e.g. infection, pain, etc.), however, the participation in this study is not associated with any additional risks that would not otherwise be encountered during the normal progression of treatment for this condition. The hernia repair will follow standard of care with one of two FDA cleared hernia repair implants for their intended applications.

## V. Study Participants

Subjects will be identified by the investigators and/or personnel assigned by the investigators, as patients with a large complicated ventral hernia expected to be repaired with porcine derived dermal matrices. The inclusion criteria for subject selection are designed to broadly capture the subset of patients where surgeons are already currently using porcine derived dermal matrices. It is not intended to usurp clinical judgment, nor advocate that modifiable patient behaviors, like smoking, not be modified in order to include a subject. Rather the criteria are designed to be inclusive of patients with large, complex hernias, particularly those in patients without acute, but at greater risk for, surgical site infections.

#### **5.1 Informed Consent**

Written informed consent will be obtained from each subject before any study procedure takes place. Informed consent will be administered by the investigator (or designee).

# 5.2 Eligibility Criteria

#### 5.2.1 Inclusion Criteria

- 18 years of age or greater
- Have a BMI < or equal to 40

- Have a pre-operative estimated hernia defect of 200 cm2 OR multiple hernia defects whose combined area is ≥ an estimated 200 cm2. Patients whose defects do NOT meet or exceed 200 cm2 intra-operatively will be withdrawn from the study and will be considered an intra-operative screen failure
- Have no contraindications to the test material (s)
- Have a life expectancy greater than 1 year in the opinion of the Investigator
- Able to provide informed consent
- Able and willing to return for scheduled study visits over 2 years post-operatively (following research related surgery)

#### 5.2.2 Exclusion Criteria

- < 18 years of age

- Subject is determined to have an American Society of Anesthesiologists' (ASA) physical class of 4, 5, or 6
- Have a BMI >40
- Have a hernia estimated to be <200 cm^2
- Have abdominal loss of domain such that the operation would be impractical or would adversely
  affect respiratory or cardiovascular function to an unacceptable degree in the opinion of the
  investigator
- Participation in an investigational drug or device study that would impact the safety or scientific
  integrity of this study (in the opinion of the Investigator and with the approval of the Sponsor)
  within the past 6 weeks prior to enrollment into this trial
- Have active necrotizing fasciitis or any other known active local or systemic infection
- Have a known collagen metabolism disorder or any medical condition that could interfere with normal tissue healing process as determined by the Investigator
- Have a known active malignancy present and/or had chemotherapy 12 weeks prior to screening or planned chemotherapy within 12 weeks of enrollment with exception of BCC or SCC
- Have known moderate to severe cirrhosis which in the opinion of the Investigator would impact the outcome of this trial
- Have a life expectancy less than 1 year
- Be unable to participate in the informed consent process
- Be unable or unwilling to return for scheduled study visits over the 2 year post-operative assessment period
- Received high dose steroids (>-100mg of prednisone) within the past 6 weeks
- Known tobacco use within the past 6 weeks or positive serum cotinine test at time of admission (patients who chew tobacco may be included at the discretion of the surgeon)
- Uncontrolled diabetes (i.e. known HbA1C value > 7% within the last 6 weeks)
- History of drug addiction (recreational drugs, prescription drugs or alcohol) that in the Investigator's opinion may interfere with protocol assessments and/or the subject's ability to complete the required follow up
- Pregnancy and/or breastfeeding

- Enterocutaneous fistula
- Ventral hernia repairs involving active infection
- Planned use of external VAC dressing intra-operatively

## 5.3 Enrollment and Subject Number Identifiers

#### 5.3.1 Enrollment

Upon signing an approved Informed Consent Form subjects will be assigned a unique subject number.

#### 5.3.2 Randomization

Patients who are consented and enrolled in the study will be randomized to receive either one of the two hernia repair implant interventions. Randomization will be 1:1. Patient numbers were allocated to a study arm based on pre-established randomization tables. Randomization tables were created using ranblock.exe (Menne Biomed Software, Tübingen, Germany). Sealed envelopes were prepared with patient specific numbers and provided to the site. If a patient is withdrawn after they have been assigned a number, the envelope with the corresponding patient number will be considered non-transferable and may not be forwarded to another patient. The subject will be blinded to their treatment arm, but the surgeon will not.

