#### III. Statistical Design

This study is a single-center prospective, randomized study evaluating Fortiva Porcine Dermis vs. Strattice Reconstructive Tissue Matrix in complex hernia repair. Up to 120 total subjects will be randomized in a 1:1 ratio.

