## The physician should NOT disclose the treatment to the subject.

Having the investigator blinded to the treatment assignment prior to randomization reduces enrollment bias.

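### The plan does not fix whether the envelope is opened before or after the intra-operative exits, so patients could be excluded with knowledge of the arm; guessing from past allocations is a smaller, conditional risk

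*Combined protocol and SAP*

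**What the plan says.** Section 5.3.1: "Upon signing an approved Informed Consent Form subjects will be assigned a unique subject number". Section 5.3.2 then says "Patient numbers were allocated to a study arm based on pre-established randomization tables", "Randomization tables were created using ranblock.exe" and "Sealed envelopes were prepared with patient specific numbers and provided to the site". An envelope whose patient is withdrawn after numbering may not go to another patient; whether it is opened is not stated. On blinding, "The subject will be blinded to their treatment arm, but the surgeon will not". Section III adds "This study is a single-center prospective, randomized study".

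The safeguard offered, in the note that follows 5.3.2, is this: "Having the investigator blinded to the treatment assignment prior to randomization reduces enrollment bias".

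Section 6.1 places the eligibility review at Visit 1, after consent. Section 6.2 allows up to 60 days from baseline to surgery. Three exits are decided in the operating room: defect below 200 cm² (5.2.1), active infection (6.2.1), and abdomen not closable (6.2.1 and 2.2). Section 2.2 puts the randomisation step after the text on mobilising the abdominal wall.

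The plan does not state whether the list is blocked, the block size, who holds and opens the envelopes, or when. No stratification or central release is described.

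**The concern.** Concealment has to last until the decision to include the patient is final. Under 5.3.1 and 5.3.2 the arm is settled at consent and the matching envelope is on site, while several inclusion decisions are still open. Some of these rest on judgement: loss of domain, conditions that impair healing and chewing tobacco (5.2.2), and in theatre the defect size and closure. If the envelope is opened before they are made, a difficult case could be kept or dropped according to the implant assigned, and no guessing is needed.

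An exit of this kind removes the patient from the comparison. Section 2.2 keeps data on closure failures out of the primary analysis, and 5.3.4 lets the sponsor replace subjects who discontinue. The intention-to-treat analysis in 3.2 cannot recover a patient who was screened out or never approached. Blinding the patient and the independent evaluator does not help either, because the imbalance arises before any outcome is assessed.

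A second route is prediction. A 1:1 blocked list returns to balance at the end of each block, so someone who knows all past allocations can bet on the arm that is behind.

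**Working it through.** **1. Order of events**

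| Step | Sections 5.3.1, 5.3.2, 6.1 | Section 2.2 |
|---|---|---|
| Arm attached to patient | At consent, through the number | After the mobilisation text |
| Eligibility review | Afterwards, at Visit 1 | Already done |
| Size and infection exits | Afterwards, in theatre | Not placed relative to randomisation |
| Closure judged obtainable | Afterwards, in theatre | In the text following randomisation |
| Envelope opened | Not stated | Not stated |

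The first column leaves every exit after the arm is fixed. The second moves randomisation later but still does not put it after all the exits. The documents give no count of exits, so the bias by this route cannot be calculated.

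**2. Guess rate if the list is blocked**

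The plan gives no figure to reproduce. Inputs: ratio 1:1 (5.3.2). Assumptions: permuted blocks of size 2b, and every earlier allocation known. Guessing the arm that is behind, with a coin toss when tied, is correct on average in a share

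g = [b + (4^b / C(2b,b) − 1)/2] / (2b).

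For blocks of 4 (b = 2): [2 + (16/6 − 1)/2]/4 = 2.833/4 = 70.8%.

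If the block size is known, the share of assignments known with certainty is 1/(b+1).

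| Block size | 2 | 4 | 6 | 8 | 10 |
|---|---|---|---|---|---|
| g, all earlier allocations known | 75.0% | 70.8% | 68.3% | 66.6% | 65.3% |
| Certain, size known | 50% | 33% | 25% | 20% | 17% |
| g, one preceding allocation unknown | 50% | 58% | 60% | 60% | 60% |
| g, three unknown | 50% | 50% | 53% | 55% | 56% |
| g, 10% unseen, size known | 72.5% | 68.1% | 65.5% | 63.8% | 62.6% |

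Check of the third row for blocks of 4: the four positions give 1/2, 1/2, 2/3 and 2/3, mean 58.3%. If 10% of envelopes are never seen and the block size is unknown, simulation gives about 58% for blocks of 4 to 8; with 20% unseen, about 56%. Randomly mixed blocks of 4, 6 and 8 with full knowledge give 68.0%. Blocks of 20 give 61.7%, and an unrestricted list gives 50%.

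**3. Illustrative bias from guessing**

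Assume identical implants, half the candidates at low risk and half at high risk, and a suitable patient always available. Let s be the share of unequal-tally slots that are deliberately steered. Correct guesses exceed wrong ones by 2g − 1 of all slots, so

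spurious difference = s × (2g − 1) × (high risk − low risk).

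Blocks of 4, full knowledge, 2g − 1 = 0.417:
- Assumed risks 20% and 40%: 0.417 × 20 = 8.3 points at s = 1, and 4.2 at s = 0.5. Simulated Fisher false-positive rate at s = 1: about 11–13%, against about 3% with no steering.
- Risks 18% and 50%: 0.417 × 32 = 13.3 points at s = 1, and 6.7 at s = 0.5. False-positive rate at s = 1: about 27%.

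Blocks of 4, one earlier allocation unknown, 2g − 1 = 0.167: 3.3 and 5.3 points at s = 1, with a false-positive rate of about 5% in the first scenario. With 10% of envelopes unseen and block size unknown, the first scenario gives 3.4 points and about 5%.

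**The case against.** Sealed, numbered envelopes are a recognised form of concealment, and the protocol states the aim of keeping the investigator unaware beforehand. That is fair, but a stated aim does not fix when an envelope is opened, and two parts of the plan give different orders of events.

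A reader might infer that the site can in practice guess the next implant 65–75% of the time. The documents do not support that. No section says the list is blocked; the only hint is the program's name. The block size is assumed. The range needs every earlier allocation to be known in sequence, yet surgery may follow baseline by up to 60 days, so at consent some earlier patients may not have been operated on. Envelopes of withdrawn patients may stay unopened, which spoils the running tally for anyone who does not know the block size. Sections V and 5.1 also let assigned personnel identify and consent subjects, and nothing shows that whoever enrols tracks the sequence. The lag does weigh less for the intra-operative exits, because by then more of the earlier-numbered patients may have had surgery.

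A reader might also infer that a bias of 8 or 13 points is to be expected. It is not. Those figures require full knowledge, blocks of 4 and deliberate steering at every opportunity. The 18% and 50% are the ends of a range of reported recurrence rates in 2.2, not two risk groups within this trial. Nothing in the documents shows that steering has occurred or is intended, and Section XVI reports no known conflict of interest.

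**Conclusion.** The point holds as a gap in allocation concealment. The arm is tied to a number given at consent, the envelopes are on site, later exits are judged with an unblinded surgeon present, and the plan does not place the opening of the envelope before or after them. Arm-aware exclusion is therefore possible. This rests on the text alone and needs no assumption about blocking, but its size cannot be estimated.

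Prediction is secondary and conditional: 65–75% correct guesses if blocks of 2 to 10 were used and all earlier allocations are known; about 50–60% with one unknown; about 58% with 10% of envelopes unseen and the block size unknown. The bias figures of about 4 to 13 points, with a false-positive rate of up to 27%, are illustrative ceilings for blocks of 4 under assumed risks and deliberate steering. They are not forecasts. The change is a cheap improvement worth making for all envelopes not yet opened.

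**What to change.** Amend 5.3.2 for all unopened envelopes:

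1. Keep the subject number given at consent as an identifier only, with no arm attached.
2. Hold the list off site and release the next assignment one at a time, only after the pre-operative and intra-operative eligibility items are recorded (defect size, infection status, primary closure judged obtainable).
3. Reconcile 2.2 with 5.3.1 and 5.3.2 so that one order of events stands.
4. State whether the list is blocked. If the remaining list is, regenerate it with randomly varying block sizes not disclosed to the site. This removes most assignments known with certainty but leaves guessing near 68%, and off-site release alone does not stop guessing from the tally.

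An unrestricted 1:1 list would make the tally uninformative, but it is optional because it gives up balance. With 120 patients the 95% range is about 49:71 to 71:49. Taking the plan's 80% power as given, power becomes 79.7% on average and 78.6% at 49:71.

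The cost is one amendment and one call or message per case, with no extra patients. One limit remains: 2.2 also withdraws a patient if the fascia cannot be fully closed over an implant already placed. That exit stays after allocation under any order and has to be settled with the analysis population in 3.2.

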## The physician should NOT disclose the treatment to the subject.

Having the investigator blinded to the treatment assignment prior to randomization reduces enrollment bias.

# 5.3.3 Subject Withdrawal and Discontinuation

Subjects may withdraw consent to participate at any time during the study for any reason. The Investigator may also withdraw a subject from the study if the subject:

- i. Is in deviation of the protocol
- ii. Experiences a serious or intolerable AE
- iii. Develops symptoms or conditions listed in the exclusion criteria during the course of the study
- iv. Requests an early discontinuation for any reason

Information regarding all withdrawn or lost-to-follow-up subjects will be documented on the Study Disposition Form. Patients will either complete all the necessary study requirements or their participation in the study may prematurely end for one or more reasons. Patients will be considered "Withdrawn" due to: death, a concurrent illness that prohibits continued participation, the Investigator elects to withdraw the participant due to reasons listed above or because he/she voluntarily withdraws consent at any time during the study for any reason. Such withdrawals shall be documented on the Study Disposition Form. All available information concerning death or concurrent illness should be documented and evaluated for adverse event reporting. If the participant withdraws his/her consent, he/she should be asked (when possible and without coercion) the reason for the decision and notified that data already collected will continue to be

part of the study as per the consent form he/she signed at the time of enrollment. No further study procedures will take place after the participant requests to be withdrawn from the study.

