#### **II. Study Design**

This is a randomized, prospective, double-blinded study evaluating the efficacy of Fortiva Porcine Dermis versus Strattice Reconstructive Tissue Matrix in 120 patients with large complex abdominal wall ventral hernias undergoing single stage repair. The patient will be blinded to treatment as well as an independent qualified evaluator to confirm evidence of reoccurrence. This post-market study compares two FDA cleared biologic hernia materials. Fortiva™ porcine dermis, processed by RTI Surgical, Inc., a non-cross linked porcine dermis will be compared to Strattice™ Reconstructive Tissue Matrix by LifeCell, a non-cross linked porcine dermis for reinforcement during the single stage open reconstruction of abdominal wall defects. The primary outcome will be hernia recurrence at 1 year. Outcomes will be evaluated at 6 weeks, 3 months, 6 months and 12 months and 24 months.

#### 21 CFR 812

As devices that have been cleared for marketing and being investigated in accordance with its cleared indications and cleared labeling, the Study entitled "A Randomized, Prospective Study Comparing Fortiva vs. Strattice in Patients Undergoing Open Primary Ventral Hernia Repair" is exempt from IDE regulations according to 21 CFR 812.2(c) (2).

A device, other than a transitional device, introduced into commercial distribution on or after May 28, 1976, that FDA has determined to be substantially equivalent to a device in commercial distribution immediately before May 28, 1976, and that is used or investigated in accordance with the indications in the labeling FDA reviewed under subpart E of part 807 in determining substantial equivalence.

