## 2.4.2 Secondary Endpoints

- Recurrent hernias (functional hernias) requiring surgical intervention
- True recurrence at 24 months
- Evidence of Eventration/Hernia Recurrence (Radiographic)
- Fluid collection (Seroma, Hematoma)
- Surgical Site Infections
- Systemic Infections
- Enterocutaneous Fistula
- Dehiscence
- Implant failure requiring partial or total removal
- Patient satisfaction (using the SF-36 questionnaire) at Baseline, 3 months, 6 months, 12, and 24 months.
- Days to discharge
- Pain measured using the Visual Analog Scale for discomfort at Baseline, 3 months, 6 months, 12 months, and 24 months.
- Patient contentment with the cosmetic results at 12 months, 24 months and/or at the time of study withdrawal except for patients who have been withdrawn due to recurrence.

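### Section 5.3.3 lets the investigator withdraw an implanted patient for a complication, and nothing requires recurrence status at or after that exit

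*Combined protocol and SAP*

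**What the plan says.** Section 5.3.3 gives the investigator discretion to withdraw a subject who deviates from the protocol (reason i), who "Experiences a serious or intolerable AE" (reason ii), or who "Develops symptoms or conditions listed in the exclusion criteria during the course of the study" (reason iii). It adds that for patients "their participation in the study may prematurely end for one or more reasons", and it lists "a concurrent illness that prohibits continued participation" as a further ground. On records it says: "Information regarding all withdrawn or lost-to-follow-up subjects will be documented on the Study Disposition Form". It rules out further study procedures after a participant's own request to leave. It says nothing about follow-up after an investigator's decision.

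The exclusion list in section 5.2.2 contains "Have active necrotizing fasciitis or any other known active local or systemic infection" and, separately, enterocutaneous fistula. Section 2.4.2 makes "Surgical Site Infections", systemic infections and enterocutaneous fistula secondary endpoints.

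On blinding, section II states: "The patient will be blinded to treatment as well as an independent qualified evaluator to confirm evidence of reoccurrence". Section 5.3.2 says that the surgeon is not blinded and describes investigator blinding only before randomization. Section 2.2 has the investigator placing the implant.

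For early withdrawal, the only assessment named in the schedule of events (section 6.10) is the cosmetic-contentment form. Section 3.2 analyses patients by assigned arm whatever their compliance or withdrawal. It does not say how a missing 12-month outcome is handled.

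**The concern.** Implantation is a single act. Withdrawing a patient afterwards removes no exposure to the implant and ends only observation. The permitted reasons include complications that the trial counts as outcomes and that may well predict recurrence. The decision rests with someone who appears to know the arm, and the blinded evaluator has no stated part in it.

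The primary endpoint is true recurrence at or before 1 year (section 2.4.1). If patients leave for reasons linked to recurrence, those who remain no longer represent the randomized groups. Section 3.1 bases the sample size on a log-rank test. Censoring at withdrawal in such an analysis would assume that withdrawal is unrelated to later recurrence, and reasons ii and iii make that assumption doubtful. The allowance of 15 to 20% dropout protects power but not against this kind of bias.

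**Working it through.** **What can be reproduced.** The 60 per arm in section 3.1 cannot be re-derived, because no recurrence proportion, hazard rate or hazard ratio is given. The documents also give no withdrawal rate, complication rate or recurrence rate among complicated patients. What follows is therefore a bound plus scenarios on assumed rates.

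**Bounds.** With 60 per arm, one unknown 12-month status widens that arm's recurrence bounds by 1/60 = 1.7 points. With m unknown in each arm, the difference is uncertain by ±m/60:
- m = 3: ±5.0 points.
- m = 9 (15% of 60): ±15.0 points.
- m = 12 (20% of 60): ±20.0 points.

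The last two lines cover dropout from every cause. Investigator withdrawals are only part of it.

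**Unequal withdrawal, equal true recurrence.** Let p be the proportion with a complication, rc their recurrence risk, r0 = 0.15 the risk in the others, and w the proportion of complicated patients withdrawn. All four are assumed. Recurrence among completers is

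[(1−p)·r0 + p·(1−w)·rc] / [1 − p·w].

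For the mild case at w = 0.75: (0.85×0.15 + 0.15×0.25×0.25)/(1 − 0.1125) = 0.1542. At w = 0.25: 0.1617. The false difference (arm with less withdrawal minus arm with more) is 0.7 points.

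| Case | p | rc | False difference, w 40% vs 20% | False difference, w 75% vs 25% |
|---|---|---|---|---|
| Mild | 0.15 | 0.25 | 0.3 | 0.7 |
| Middle | 0.20 | 0.35 | 0.7 | 2.0 |
| Strong | 0.30 | 0.50 | 1.8 | 5.1 |

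The standard error of the difference at 20% recurrence is √(2×0.2×0.8/60) = 0.073, or 7.3 points. Every entry is below that. With equal complications and equal withdrawal the difference is zero.

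The 5.1 needs 60×0.30×0.75 = 13.5 patients withdrawn by the investigator in one arm. That is 22.5%, above the 15 to 20% planned for all causes.

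**Partial capture through late serious adverse events (section 7.3).** If a fraction c of withdrawn patients' recurrences is still reported, add p·w·rc·c to numerator and denominator. For 75% vs 25%, mild, middle and strong in turn:
- c = 0.5: −0.2, 0.2 and 1.1 points.
- c = 1: −1.0, −1.4 and −2.2 points.

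The sign reverses because recurrences come back into the data and recurrence-free status does not.

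**Unequal complications, equal withdrawal.** Take p = 0.20 vs 0.40 with half of complicated patients withdrawn in both arms, leaving 54 and 48. The upper 90% limit is the difference + 1.645 standard errors.

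| rc | True difference | Observed difference | Upper 90% limit, full data | Upper 90% limit, after loss |
|---|---|---|---|---|
| 0.25 | 2.0 | 1.4 | 13.5 | 13.6 |
| 0.35 | 4.0 | 2.8 | 16.2 | 15.5 |
| 0.50 | 7.0 | 4.9 | 20.0 | 18.2 |

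The observed difference shrinks by about 30% in each row. The limit barely moves in the first row and falls in the other two.

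**The case against.** The best defence is that the plan does not intend complicated patients to leave. The withdrawal power is discretionary. Reason iii has an obvious use before implantation: eligibility is reviewed again on the day of surgery (section 6.2), and infection found at operation makes the patient a screen failure (section 6.2.1). Visits 3 to 7 list infection, fistula and graft failure as events to evaluate at continuing visits, with a recurrence examination each time, so status is known up to withdrawal.

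Other provisions also help. Section 6.9 suggests a recurrence check at unplanned visits. Section 7.2 promises every effort to follow the subject until the event resolves. Section 7.3 records later serious events where a causal link cannot be excluded. Section 2.4.2 exempts patients withdrawn for recurrence from the cosmetic form, which presupposes that this exit reason is known. The fields of the Study Disposition Form are not shown. The final report must already cover withdrawals (section XIV).

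Much of this stands, and it limits how often the problem should arise. It does not close the gap. The wording of reason iii also reaches events after implantation. Unplanned-visit procedures are only suggested and are not tied to withdrawal. Section 7.2 concerns the adverse event, not recurrence. The route in section 7.3 is passive: it may pick up a recurrence that leads to admission, but it never shows that a patient is recurrence-free. Whatever the Disposition Form holds, no section requires recurrence status on it.

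The scenario formula also gives withdrawn patients no credit for recurrences found before exit, or for recurrence-free time that a log-rank analysis would count. Its results therefore lie towards the high side.

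**Conclusion.** The gap is real and worth closing. Following section 5.3.3 as written can lose the 12-month primary outcome for reasons plausibly linked to it. Bias requires that withdrawal be related to recurrence risk and that either withdrawal or complications differ by arm. Its size and direction are unknown. On the assumed rates it runs from about −2 to 5 points, mostly a few points, always below one standard error.

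Three stronger readings are tempting and are not supported:
- A reader might infer that an unblinded investigator will remove patients selectively. The documents make the surgeon unblinded and show the investigator operating, but they never state outright that the person deciding on withdrawal knows the arm. Nothing indicates selective use.
- A reader might attribute the ±15 to 20 points to this rule. That range belongs to dropout from all causes.
- A reader might conclude that the loss favours the equivalence finding to which section 3.2 turns if superiority is not shown. The observed difference does shrink when complications truly differ, but the smaller sample widens the interval. In the mild case the upper limit is 13.6 against 13.5. No equivalence margin is stated, so the effect on that conclusion is unknown.

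**What to change.** In section 5.3.3, state that for implanted patients who are not intra-operative screen failures, investigator withdrawal for reasons i to iii does not end outcome follow-up. Recurrence assessment continues at the contacts already scheduled until recurrence is diagnosed, unless the patient withdraws consent, dies, is lost to follow-up or cannot attend. Any exit for concurrent illness should carry a specific documented reason and should not be used merely because an endpoint complication occurred.

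Extend the early-withdrawal footnote in section 6.10 so that recurrence status and its date are recorded at any early exit, where the patient agrees. Align the follow-up definition for withdrawn subjects in section 7.3 and keep its rule on later serious events. Add to section XIV a report of exits by arm and reason. Pre-specify one sensitivity analysis for missing 12-month status, for example a tipping-point table by arm.

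The cost is protocol wording and some extra visit and case-report-form work. Recurrence up to 12 months is assessed by physical examination, so a telephone call cannot replace the visits. At most four face-to-face visits after discharge are involved (6 weeks, 3, 6 and 12 months). At up to $100 travel each (section XV) that is 4 × $100 = $400 per retained patient, plus the 24-month call. Clinical care does not change.
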